7. CLINICAL INVESTIGATION DESIGN

7.1 Trial Design

Investigator-initiated, academic, mono-center, prospective, field observation study using a novel CE-labeled surgical platform.

The study will be terminated after a time period of three months. A maximum of 250 patients will be enrolled. The study will consist of 3 patient visits. Study follow-up is 1 day after the date of the vitrectomy surgery.

During surgery, intra-operative complications and issues will be recorded for safety assessment: see list in previous paragraph.

Typical postoperative follow-up after vitrectomy includes the clinical tests to assess that normal postoperative outcome is present, without the presence of adverse events.

Hence, the same clinical data will be collected in the study patients as in patients undergoing the standard-of-care.

This field observation study is conducted to obtain information about the complication rate of the EVA Nexus system which will be compared with the incidence of these complications occurring in surgeries performed using our present DORC EVA platform. ¹⁵⁻¹⁸

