4. CLINICAL INVESTIGATION SUMMARY

Title	EVA Nexus Field Observation Study
Reference Number (Acronym)	EVA Nexus
Clinical Phase	Non applicable
Objectives	To perform a field observation study using the newly developed EVA Nexus vitrectomy device.
Endpoints	Primary endpoint: determine the safety and effectiveness of the device.
Design	Investigator-initiated, mono-center, academic, prospective, observational case study
Data Collection	
Total duration of study for each patient will be 2 days (from surgery date to last follow-up day)
 
See Study Flow Chart 7.3

Planned Clinical investigation Period	Q2-Q3 2021
Clinical investigation population	
Patients that are scheduled for intra-ocular surgery regardless of the indication:
 
 • Vitrectomy surgery • Cataract surgery • Vitrectomy combined with cataract surgery
Number of Participants	Up to 250, inclusion period of three months.
Inclusion/Exclusion Criteria	
Inclusion criteria
 
 • Patients that are scheduled for intra-ocular surgery regardless of the indication: 
 • Vitrectomy surgery • Cataract surgery • Vitrectomy combined with cataract surgery • In case of (combined) vitrectomy: primary or repeat vitrectomy • General or retrobulbar anesthesia, the latter can be combined with sedation • Patients aged \geq 18 years 
Exclusion criteria
 
 • Patients aged $<$ 18 years
Device Name	EVA Nexus (CE-labeled device)
Principle Intended Use	The device is intended to be used during ophthalmic surgery.

Manufacturer Name

DORC B.V.

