6. OBJECTIVES

The primary objective and primary parameters are shown in the table below:

The main purpose of this study is to evaluate the intra-operative safety of a new surgical device.
	
Therefore, having no idea of the percentage of patients having complications, we make the hypothesis that minimum 5% of the patients will have complications. In order to make sure that we have at least 10 patients with complications, we plan recruit 250 patients in total in order to get at least 10 complications with EVA Nexus.
 
For this purpose, typical surgical parameters will be recorded during vitrectomy surgery:
 
 • Surgical indication • If combined phaco-surgery is performed: amount of phaco power used • Staining dyes (if used) • Amount of laser coagulates (if used) • Type of tamponade left in the eye: BSS+ liquid, air bubble, air, gas (type + concentration) or silicone oil (type) 
Specific adverse events that may occur during (phaco)vitrectomy will be recorded to assess the surgical safety ¹⁵⁻¹⁸: see list in Appendix A. This AE reporting is already present in the surgical report (KWS-Formasa) used for daily vitrectomy surgery using the DORC EVA device. The occurrence of these AE's during surgeries using the EVA Nexus will be compared to historical data retrieved from surgeries using the DORC EVA platform.
 
Device issues that caused some hindering during the surgery but that do not lead to an (S)AE, such as error messages/warnings that did occur, malfunctioning of supplies that required replacement etc. will be recorded.
 
See Appendix B for a full list, which is already part of our present surgical report (KWS-Formasa). The occurrence of these issues during surgeries using the EVA Nexus will be compared to historical data retrieved from surgeries using the DORC EVA platform.

---	---

The secondary objective and secondary parameters are shown in the table below:

Secondary objective	Secondary parameters
To evaluate the possible reduction of total surgical time.	The time that was required to prepare the EVA Nexus will be recorded (connecting of supplies + priming). During the study period, this time will also be recorded during surgeries performed with the DORC EVA device for comparison.

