8. CLINICAL INVESTIGATION POPULATION

8.1. Number of participants – sample size analysis

With a complication rate ranging from 5% up to 30% in previous studies, we have no a priori about the complication rate of the EVA Nexus system. We therefore consider a rather conservative hypothesis and expect to have around 5% of complications with the EVA Nexus system. We plan recruit 250 patients in total in order to get at least 10 complications with EVA Nexus. The estimated enrolment time is 6 months.

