13.2. The number of participants

Maximum 250, inclusion time 4 months.

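### Three enrolment periods (three, four and six months) are stated for the same 250 patients, and the three-month closing rule in section 7.1 is not reconciled with the six-month estimate in section 8.1

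*Combined protocol and SAP*

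**What the plan says.** Four places in the combined protocol and SAP give a duration for the same number of patients.

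- Section 4 (summary): "Up to 250, inclusion period of three months".
- Section 7.1: "The study will be terminated after a time period of three months. A maximum of 250 patients will be enrolled".
- Section 13.2: "Maximum 250, inclusion time 4 months".
- Section 8.1: "The estimated enrolment time is 6 months".

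The number itself is justified in two places. Section 8.1 says "We plan recruit 250 patients in total in order to get at least 10 complications with EVA Nexus", having stated that the investigators "expect to have around 5% of complications with the EVA Nexus system". Section 6 gives the same reason with a different reading of the rate: "we make the hypothesis that minimum 5% of the patients will have complications", followed by "In order to make sure that we have at least 10 patients with complications, we plan recruit 250 patients in total". No other justification for 250 appears.

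The amendment history in section 1 has no entries, so none of the periods is marked as superseded. Follow-up is one day after surgery (section 7.1). Section 4 places the investigation in Q2-Q3 2021. No section gives an expected number of patients per month.

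**The concern.** The four statements cannot all describe one enrolment plan. Sections 4 and 13.2 both describe the inclusion period and differ by a month. Section 7.1 is a closing rule, and it falls at half the time that section 8.1 expects recruitment to take. A distinction between enrolment time and total study time does not explain the gap, because follow-up adds only one day per patient.

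What is at stake is the sample size rationale. If enrolment closes before 250 patients are reached, the chance of seeing at least 10 complications falls, and so does the power of the planned one-sample comparison with the literature rates (section 13.1). Also, in an open single-arm study without a steering or data monitoring committee (sections 14.2 and 14.3), closure at three, four or six months could each be defended from the text. It is better to fix the stopping point in advance.

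**Working it through.** **Inputs.** N = 250 and at least 10 complications (sections 6 and 8.1); complication rate 5% (section 8.1, and a minimum in section 6); periods of 3, 4 and 6 months (sections 4 and 7.1, 13.2, and 8.1); two-sided 5% significance level (section 13.3); benchmark of 15%, one of the three literature rates in section 13.1. Assumptions added here: constant accrual, and a binomial count of patients with complications.

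**Reproducing the plan's figure.** Expected complications are 250 × 0.05 = 12.5. The exact binomial probability P(X ≥ 10) with n = 250 and p = 0.05 is 0.805. The smallest n with P(X ≥ 10) of at least 0.80 at 5% is 249, so 250 is consistent with about 80% assurance. The documents state no probability, so the 80% is inferred. Simple division, 10/0.05 = 200, does not give 250.

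**Pace implied by each period.**

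- 250/3 = 83.3 patients a month
- 250/4 = 62.5 patients a month
- 250/6 = 41.7 patients a month

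**Patients enrolled at a three-month stop, by pace.**

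- Section 8.1 pace: 250 × 3/6 = 125
- Section 13.2 pace: 250 × 3/4 = 187.5, taken as 188
- At 83.3 a month: 250

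**Expected complications and chance of at least 10.**

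| n | Expected at 5% | P(X ≥ 10) at 5% | at 10% | at 15% |
|---|---|---|---|---|
| 125 | 6.25 | 0.097 | 0.813 | 0.994 |
| 188 | 9.4 | 0.467 | 0.993 | >0.999 |
| 250 | 12.5 | 0.805 | >0.999 | >0.999 |

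With 125 patients the true rate would have to be about 9.9% to give the assurance that 250 patients give at about 5%.

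**Precision.** For an observed 4.8%, the exact (Clopper-Pearson) 95% interval is 1.8% to 10.2% with 6/125 and 2.5% to 8.2% with 12/250.

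**Power against the 15% benchmark** (exact two-sided one-sample test, 5% level).

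| True rate | n = 125 | n = 250 |
|---|---|---|
| 5% | 0.95 | >0.999 |
| 10% | 0.28 | 0.63 |

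The smaller sample costs this comparison little at a true 5%, but more than half of its power at a true 10%.

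**The case against.** The strongest reply is that a time limit combined with a cap of 250 is a coherent closing rule. Sections 4, 7.1 and 13.2 all call 250 a maximum, and planning for 250 while never exceeding it is not a contradiction. That stands. The inconsistency lies in the durations, and in the absence of any statement on whether time or number governs closure.

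Second, no section yields 125 patients. That figure joins the stop in section 7.1 to a pace inferred from an estimate in section 8.1. This also stands: if section 8.1 is the wrong entry, three months could deliver all 250. A reader might infer that the study will enrol only 125 patients, or is bound to miss its 10 complications. The documents do not support that, because they give no recruitment rate that would favour one period over another.

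Third, the loss at 5% is the low end of the plan's own range. Section 6 calls 5% a minimum, and section 8.1 cites 5% to 30% from previous studies. At a true 10%, even 125 patients give an 81% chance of at least 10 complications. This limits the consequence for the event target, but the power loss against 15% at that same rate remains.

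Finally, this is probably unreconciled drafting, and patient care is not affected, since section 9.1 keeps care the same whether or not a patient takes part. That bears on severity. It does not tell a reader which period applies.

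**Conclusion.** The mismatch of periods is certain: current text gives three, four and six months for the same 250 patients, with nothing to reconcile them. It should be fixed, because section 7.1 is the rule that closes the study and 250 rests only on reaching 10 complications.

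The shortfall is conditional. It arises if, and only if, the three-month stop is applied and the section 8.1 pace is right, with constant accrual. In that case the chance of at least 10 complications at 5% falls from about 80% to about 10%. At the section 13.2 pace it would be about 47%. If about 83 patients a month is realistic, there is no shortfall, and the entries to correct are those in sections 8.1 and 13.2.

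A minor point of wording goes with this. Section 6 presents 250 as securing at least 10 patients with complications, but at 5% about one such study in five would fall short. If 5% is truly a minimum, 80% is a lower bound.

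**What to change.** State one enrolment period, supported by the site's expected monthly recruitment, and one closing rule (250 patients, the time limit, or whichever comes first), in identical terms in sections 4, 7.1, 8.1 and 13.2. The choice of period is the sponsor's and should follow from recruitment figures, without presuming that any one of the present entries is right.

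- If the time limit is expected to yield fewer than 250 patients, restate the expected numbers of patients and complications in sections 6 and 8.1.
- If three months is expected to yield 250, correct sections 8.1 and 13.2.
- If the period becomes six months, check it against Q2-Q3 2021 in section 4. Two quarters are exactly six months, which leaves no slack for a start that depends on the CE label (section 9.1) and ethics approval (section 14.3, Ethics review).
- In section 6, replace the language of certainty with the assurance for the number chosen: with 250 patients, about 80% at a 5% rate, and higher if 5% is a minimum.

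The cost is wording in up to five sections, with no added procedures and no patients beyond 250. Depending on the choice, the sponsor accepts either a longer enrolment window or a smaller stated sample.

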7.2 Study Flowchart

	Preop (inclusion)	Surgery	Postop day 1
Vitrectomy		X	
Visual acuity	X		X
Eye pressure	X		X
Biomicroscopy	X		X
Ophthalmoscopy	X		X
OCT	X ¹		
Ultrasound	X ²		X ²
Adverse events	X ³		X
Surgical summary		X	

X¹ if required, depending on indication for surgery, e.g.: macular pucker, macular hole, vitreomacular traction, ...

X² if required, depending on indication for surgery, e.g.: vitreous hemorrhage

X³ any pre-operative clinical condition that is known to affect the incidence of (S)AE's during surgery (e.g. zonular dehiscence, tamsulosine medication, axial length, ...)

8. CLINICAL INVESTIGATION POPULATION

8.1. Number of participants – sample size analysis

With a complication rate ranging from 5% up to 30% in previous studies, we have no a priori about the complication rate of the EVA Nexus system. We therefore consider a rather conservative hypothesis and expect to have around 5% of complications with the EVA Nexus system. We plan recruit 250 patients in total in order to get at least 10 complications with EVA Nexus. The estimated enrolment time is 6 months.

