13. STATISTICS

13.1. Description of statistical methods

Will be outsourced to a licensed medical statistician (Ars Statistica). An pseudonymizedExcel-export will be generated from the eCRF for statistical analysis.

For the primary endpoint (complication rate of the EVA Nexus), a one-sample proportion test will be performed to test whether the obtained rate is different from rates found in the literature (30%, 15% and 5%).

For the remaining data (demographics and secondary objectives), group comparisons (no complications vs complications) of categorical variables will be analyzed using a Fisher's exact test and group comparisons (no complications vs complications) of continuous variables will be performed using the T-test or the Wilcoxon signed rank test, as appropriate (=when the normality of the residuals and the equality of the variances are met, the T-test will be used, and when the normality of the residuals or the homoskedasticity of the variances will not be met, the Wilcoxon signed rank test will be used). Last, in order to test a first predictive model, a logistic or Poisson regression, as appropriate, with backward selection method will be performed, starting with all variables associated with the target with a p-value lower than 0.1. The final model will contain variables associated with the outcome with a p-value lower than 0.05.

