13.13.2. Primary outcome

For the primary endpoint (complication rate of the EVA Nexus), a one-sample proportion test will be performed to test whether the obtained rate is different from rates found in the literature (30%, 15% and 5%).

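### The primary comparison with 5% uses the rate the plan itself expects, and with no confidence interval, margin or reading rule it cannot say how high the complication rate could be

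*Combined protocol and SAP*

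**What the plan says.** Section 6 gives the aim: "The main purpose of this study is to evaluate the intra-operative safety of a new surgical device".

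The planning rate appears twice, in different words. Section 8.1 says "With a complication rate ranging from 5% up to 30% in previous studies, we have no a priori about the complication rate" and then "We therefore consider a rather conservative hypothesis and expect to have around 5% of complications with the EVA Nexus system". Section 6 treats 5% as a floor: "we make the hypothesis that minimum 5% of the patients will have complications".

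The sample size rests on a count of events: "We plan recruit 250 patients in total in order to get at least 10 complications with EVA Nexus". Section 13.2 makes 250 a ceiling: "Maximum 250, inclusion time 4 months". Sections 4 and 7.1 also give 250 as the most that will be enrolled.

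The primary analysis is a one-sample proportion test "to test whether the obtained rate is different from rates found in the literature (30%, 15% and 5" percent. It is worded the same way in sections 13.1, 13.13.2 and 13.13.3. Section 13.3 sets a two-sided 5% level for all analyses. The variant of the test (exact or normal approximation) is not named.

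The documents state no power, no alternative rate, no margin or acceptable upper limit, no confidence interval for the primary rate (the summary statistics in 13.13.1 include none), and no rule for reading a non-significant result.

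**The concern.** One of the three null values equals the planning rate in section 8.1. If that expectation is right, non-significance is the expected result of that comparison, and the plan gives such a result no meaning. A two-sided test of difference can show that a rate is not 5%. It cannot show that the rate is no higher than 5%, or no higher than any other figure.

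A safety aim asks how high the complication rate could plausibly be. Without an interval or a reading rule, that question is left until the data have been seen. A report could then say that the rate did not differ from 5%, the lowest of the three literature rates, when the data are also compatible with rates well above it.

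**Working it through.** **Inputs.** N = 250 (8.1; a maximum in 13.2). Planning rate 5% (8.1). Null rates 30%, 15% and 5% (13.1, 13.13.2, 13.13.3). Two-sided level 5% (13.3). The number of complications X is taken as Binomial(N, p), with p the true rate.

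**1. The plan's own figure.** Expected complications at 5%: 250 × 0.05 = 12.5. P(X ≥ 10) = 80.5%, and the smallest N that reaches 80% is 249. So 250 reproduces if about 80% assurance of 10 events was meant, though no level is stated. It is not a power calculation for the primary test.

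**2. When the comparison with 5% rejects (N = 250).**
- Exact minimum-likelihood test (the p-value sums every outcome no more likely than the one observed): reject at 5 or fewer, or 20 or more. The z test, with or without continuity correction, gives the same region.
- Exact doubled-tail test (matches the Clopper-Pearson interval): reject at 5 or fewer, or 21 or more.

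So the result is non-significant for 6-19 complications (2.4% to 7.6%), or 6-20 with the doubled-tail test.

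**3. If the true rate is 5%.** P(X ≤ 5) + P(X ≥ 20) = 1.3% + 2.7% = 4.0%. Doubled-tail: 1.3% + 1.5% = 2.8%. All of this is type I error. The rest, 96.0% or 97.2%, is non-significant.

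**4. If the true rate is higher.** Chance that the comparison with 5% is non-significant:

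| True rate | Minimum-likelihood or z | Doubled-tail |
|---|---|---|
| 7% | 70% | 78% |
| 7.5% | 58% | 67% |
| 8% | 47% | 56% |
| 9% | 26% | 34% |
| 10% | 12% | 17% |
| 12% | 2% | 3% |
| 15% | under 0.1% | about 0.1% |

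Power of 80% is reached only at a true rate of about 9.4% (9.8% doubled-tail).

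**5. The other two comparisons.** The exact test rejects 15% from below at 26 or fewer complications, and 30% at 60 or fewer. At a true 5% both happen with probability above 99.9%. The strongest statement they support is that the rate is below 15%. If the true rate is not 5%, even that weakens: the 15% comparison is non-significant 37% of the time at a true 10%, and 75% at 12%.

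**6. What an interval would show.** An observed 19/250 (7.6%) gives p = 0.079 by the minimum-likelihood test, so it is not significantly different from 5%. Its Clopper-Pearson 95% interval is 4.6% to 11.6%. At about the expected count, 13/250 (5.2%), the interval is 2.8% to 8.7%.

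**7. Fewer than 250 patients.** The chance of non-significance at a true 8% rises from 47% at 250 to 57% at 200 and 69% at 150. A shortfall cannot be excluded, because the enrolment period is given as three months (4, 7.1), four months (13.2) and six months (8.1).

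**The case against.** **5% is one of three null values.** A reader might infer that the primary analysis as a whole can reject only by error. The documents do not support that: at a true 5% the comparisons with 15% and 30% reject correctly and almost surely. The point is confined to the 5% comparison.

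**5% is not a firm assumption.** Section 6 makes it a minimum, and both sections say that the rate is unknown. Under the section 6 wording an upward rejection could be correct. This stands, and the two wordings should be reconciled. It does not rescue the plan: if the rate may exceed 5%, an upper bound matters more.

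**No passage calls non-significance a pass.** A reader might infer that a clearly worse device would often be passed as not different. The documents contain no such rule; the defect is that they contain no rule at all. Nor does often hold generally: non-significance is common at 7% to 8%, but has a chance of only 12% to 17% at a doubled rate of 10% and almost none at 15%. Whether 7% to 8% is clearly worse than 5% is a clinical judgement that the documents do not make.

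**This is an observational study of a CE-labelled device.** Section 7.1 describes it as gathering information on the complication rate, and the documents name no ceiling. A mandatory pass/fail limit is therefore debatable. This stands, and it is why the fix rests on the interval and leaves a ceiling optional.

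**Conclusion.** The point holds for the comparison with 5%. At the rate expected in section 8.1 that comparison ends non-significant in about 96-97% of studies, and any rejection is a false positive. The remaining comparisons bound the rate only below 15%. Nothing in the plan converts the expected non-significant result into a statement about how high the rate could be, which is what an intra-operative safety aim needs.

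The size depends on the true rate. The chance of non-significance is 58% at 7.5%, 47% at 8%, 26% at 9% and 12% at 10%, or 67%, 56%, 34% and 17% with the doubled-tail test.

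These figures assume one binary outcome per patient, independent patients, all 250 enrolled and exact binomial calculation. The plan names no test variant, so both are given. With fewer patients the figures are worse. The plan should be changed, but the change is one of wording and does not touch the design.

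**What to change.** 1. In sections 13.1, 13.13.2 and 13.13.3, make the observed complication rate with its exact (Clopper-Pearson) two-sided 95% confidence interval the primary result, and base the safety conclusion on the upper limit.
2. In the same places, state that non-significance against 5% will not be read as equal to, or no worse than, 5%. Keep the tests against literature rates as supportive at most, and name the test variant.
3. In section 8.1, state the precision that 250 patients give (for example 13/250: 2.8% to 8.7%) and note that it is worse if fewer than the maximum enrol. Reconcile the 5% wording with section 6.
4. Optional: if the sponsor wants a pass/fail statement, it should fix its own ceiling before the first patient. For illustration only, since the documents give none: an upper limit below 10% needs 15 or fewer complications in 250 (15/250 has an upper limit of 9.7%). At a true 5% that has probability 81%. The same 10% ceiling would be met with probability about 70% at 200 patients and 52% at 150.

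Cost: a few sentences, with no extra patients or data. Section 13.7 lets the statistical plan be finalised before data lock, but these changes are better made before enrolment starts. The downside is a slightly less favourable safety conclusion, because it will state an upper limit above 5%.
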